10 SAFETY ANALYSES

10.1 Extent of exposure

Summaries for exposure will be presented as the number of days exposed to study medication, number of days dose received, and the patient exposure days at risk for the Initial Period, the Maintenance Period, and the Combined Initial and Maintenance Period. For the Maintenance Period, data will be summarized separately for exposure to blinded study medication and exposure to open-label study medication. For the Combined Initial and Maintenance Period, data will be summarized separately for exposure to just blinded treatment and exposure to both blinded and open-label treatment combined. Additionally, the total patient exposure years at risk will be provided for each of the periods.

Throughout this section, date of last clinical contact for each subject is defined as the maximum of (last visit date including SFU visits, last AE start date (considering imputed dates and non-imputed dates), date of study termination or completion, last date of study drug administration) taking scheduled and unscheduled visits into account.

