10.1.1 Interim Analysis

Initial Period

Duration of exposure (days) to study medication, number of days dose received, and patient exposure days at risk during the Initial Period will be summarized by randomized treatment group for the SS, PsAS and CSS. Week 14 is the intended last administration of study medication for this period. The calculations will be as follows:

Duration of exposure:

- Date of last administration of study medication – date of first administration of study medication + 14 days

The 14 days are included in the formula as this is the dosing interval in the Initial Period.

If the date of last administration of study medication + 14 days extends to a date beyond the Week 16 study medication administration date, then this calculation reverts to:

- Week 16 study medication administration date – date of first administration of study medication.

For subjects who die during the Initial Period, if date of last administration of study medication + 14 days extends to a date beyond the date of death, then this calculation reverts to:

- Date of death – date of first administration of study medication +1.

Number of days a dose was received: The total number of dose days from Baseline (Week 0) up to Week 14 (inclusive).

Patient exposure days at risk:

For subjects who complete the Week 16 visit and continue to the Maintenance Period:

- Date of Week 16 administration of study medication – date of first administration of study medication.

For subjects who discontinue on or prior to the Week 16 visit, use the minimum of the following:

- Date of last administration of study medication – date of first administration of study medication + 70 days
- 112 days (equivalent to intended 16-week Initial Period)
- Date of last clinical contact – date of first administration of study medication + 1.

For subjects who die prior to the Week 16 visit:

- Date of death – date of first administration of study medication + 1.

Maintenance Period

Duration of exposure (days) to study medication and number of days dose was received during the Maintenance Period will be summarized by blinded maintenance treatment group for the SS, PsAS and the CSS. Week 22 is the intended last administration of study medication for this period in the interim analysis. The calculations will be as follows:

Duration of exposure:

- Date of last administration of study medication – date of Week 16 administration of study medication + 14 days

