- For subjects who discontinue on or prior to the Week 16 visit: date of Week 14 administration (or latest administration date) – date of Week 0 administration + 14 days is attributable to the original CZP treatment.
- For subjects who complete the Week 24 visit: date of Week 24 administration of study medication – date of Week 16 administration of study medication is attributable to the CZP treatment assigned at Week 16.

For subjects who discontinue on or prior to the Week 24 visit: date of latest administration of study medication – date of Week 16 administration of study medication + 14 days is attributable to the CZP treatment assigned at Week 16.

Number of days a dose was received:

For subjects who were randomized to placebo, did not escape at Week 16, and are ongoing at Week 24:

- Total number of dose days from Week 0 up to Week 22 (inclusive) is attributable to placebo.

For subjects who were randomized to placebo, did not escape at Week 16, and are not ongoing at Week 24:

- Total number of dose dates from Week 0 up to last administration of placebo is attributable to placebo.

For subjects randomized to placebo who escaped to CZP 200mg Q2W at Week 16:

- Total number of dose days from Week 0 up to Week 14 (inclusive) is attributable to placebo
- Total number of dose days from Week 16 up to Week 22 (inclusive) is attributable to CZP 200mg Q2W. Note that if a subject withdrew prior to Week 24, then this

algorithm reverts to the total number of dose days from Week 16 up to last dose of CZP.

- For subjects randomized to CZP, this is defined as the total number of dose days from date of first administration of CZP to date of last administration of CZP (inclusive). This will be calculated for CZP (regardless of dose) as well as for each individual CZP dose.

Patient exposure days at risk to placebo:

- For subjects who were randomized to placebo, did not escape at Week 16, and are ongoing at Week 24:
 - Date of Week 24 visit – date of Week 0 administration of study medication
- For subjects who were randomized to placebo, did not escape at Week 16, and are not ongoing at Week 24, use the minimum of the following:
 - Date of last administration of study medication – date of Week 0 administration of study medication + 70 days.
 - 168 days (equivalent to the intended 24-week treatment period)
 - Date of last clinical contact – date of Week 0 administration of study medication + 1 day

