If the month and year of first dose in the Maintenance Period is the same as the month and year of onset, then use the date of first dose in the Maintenance Period.

If the month and year of onset is after the month and year of first dose in the Maintenance Period, then use the 1st of the month.

If the intensity of an adverse event is unknown, it is considered as severe.

If the relationship to study drug is missing, it is considered as related.

Subject time at risk represents the time a subject was at risk for having an AE. The definitions for subject time at risk (in days) for the Initial Period, Maintenance Period, and Combined Initial and Maintenance Period are outlined in [Section 10.1](#). These definitions will be used for

exposure-adjusted AE summaries. Selected AE summaries will include the exposure adjusted incidence rate (EAIR) with associated 95% confidence interval and the exposure adjusted event rate (EAER).

For EAIR, the numerator will be the total number of subjects experiencing the AE. The denominator will be 100 subject-years; that is, the total summation of individual subject-years at risk up to the first occurrence of the AE for subjects with that AE, and the total subject-years at risk for those subjects not experiencing that AE, divided by 100. EAIRs will be presented with a 95% exact confidence interval based upon the Chi-Square distribution (Ulm, 1990).

For EAERs, the numerator will be the number of AEs including repeat occurrences in individual subjects; the denominator will be 100 subject-years. That is, the total summation of individual subject-years at risk divided by 100. No confidence interval will be computed for EAER.

Presentation Conventions

The frequency of all TEAEs during the study period will be presented by treatment group and period separately by SOC, High Level Term (HLT), and preferred term (PT). The data will be displayed as number of subjects experiencing the AE, percentage of subjects, and number of AEs, sorted by descending frequencies of PTs in the 'All CZP Subjects' column and ordered alphabetically for SOC, HLT and identical frequencies for PTs.

Tables for the Incidence of TEAEs – Overview and Incidence of TEAEs will be generated by TE-ADA status using the following categories:

1. TEAEs starting before 1st anti-CZP antibody positive
2. TEAE starting on or after 1st anti-CZP antibody positive
3. TEAEs for subjects who are always anti-CZP antibody negative

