- Major Cardiovascular Events (MACEs). They will be identified using the following SMQs: “Central nervous system haemorrhages and cerebrovascular conditions (SMQ)”, which includes the 3 following sub SMQs: “Conditions associated with central nervous system haemorrhages and cerebrovascular accidents (SMQ)”, “Haemorrhagic central nervous system vascular conditions (SMQ)”, “Ischaemic central nervous system vascular conditions (SMQ)” except events coding to PT “Transient ischaemic attack”. All serious TEAEs which code to a PT included in the HLT “Ischaemic coronary artery disorders” except events coding to PT “Chest Pain” or “Chest discomfort” and all serious TEAEs which code to a PT included in any of the following HLTs: “Heart Failures NEC”, “Left Ventricular Failures”, or “Right Ventricular Failures” and which also code to the SOC of “Cardiac Disorders” as Primary SOC will be included.

AE Summaries by Period

All of the presentations described above will be presented for the Initial Period. Subsets of the presentations described above will be presented for the Maintenance Period and for the Combined Initial and Maintenance Period. Details for these summaries are described below.

Initial Period

Summaries for the Initial Period will be presented by randomized treatment group (PBO, CZP 200mg Q2W, CZP 400mg Q2W, All CZP) based on the SS, PsA Set and the CSS. For these summaries, treatment-emergence is defined as follows:

- For subjects who complete the Week 16 visit and continue to the Maintenance Period, all AEs which started on or after the date of first dose of study medication and on or prior to the date of the Week 16 administration of study medication will be considered a TEAE for these summaries. The only exception to this rule is for the following types of events:
 - Those which code to a HLT of “Injection Site Reactions”
 - Those which have been designated as an Injection Reaction on the AE CRF and do not code to an SOC of “Investigations”
 - Those which have been identified as a hypersensitivity reaction or an anaphylactic reaction

When any of these events occur on the date of treatment switch at Week 16, the AE will be attributed to the treatment initiated at Week 16.

- For subjects who discontinue on or prior to the Week 16 visit, all AEs which started on or after the first dose of study medication and on or prior to the date of last administration of study medication + 70 days will be considered a TEAE for the analysis summaries.

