- If a subject discontinues prior to the Week 24 visit and has a Safety follow-up visit that extends beyond 24 weeks from the first study drug administration (ie, what would have been the Week 24 visit), then the period for TEAEs for that subject will end at 24 weeks

(160 days) from the first study drug administration for the interim analysis. Any TEAEs collected at the Safety follow-up visit occurring after the 24 week timepoint will be captured in the Final Clinical Study Report (CSR). This allows for a maximum treatment period of 24 weeks for each subject in this interim analysis.

- For subjects who complete the Week 52 visit, all AEs which started on or after the date of first dose of study medication and on or prior to the date of Week 50 administration of study medication + 70 days will be considered a TEAE for the final analysis summaries.
- For subjects who discontinue prior to the Week 52 visit, all AEs which started on or after the first dose of study medication and on or prior to the date of last administration of study medication + 70 days will be considered a TEAE for the final analysis summaries.
- For subjects who die prior to the Week 24/52 visit, all AEs which started on or after the first dose of study medication and prior to or on the date of death will be considered a TEAE for the interim/final analysis summaries.

The following AE summaries will be produced for the Combined Initial and Maintenance Periods considering just those AEs which emerged while on blinded or open-label treatment using the SS, PsAS and CSS:

- Incidence of TEAEs – Overview
- Incidence of TEAEs by TE-ADA status – Overview
- Incidence of TEAEs by TE-ADA status (Includes EAIR and EAER)
- Incidence of TEAEs by Maximum ADA Titer (Safety Set (Excluding PBO treatment group) and Cohort Safety Set combined)
- Incidence of TEAEs (includes EAIR and EAER)
- Incidence of Serious TEAEs (includes EAIR and EAER)
- Incidence of TEAEs Resulting in Permanent Discontinuation of Study Drug
- Incidence of TEAEs leading to death
- Incidence of TEAEs by Maximum Intensity
- Incidence of TEAEs by Maximum Relationship
- Incidence of Serious TEAEs by Maximum Relationship
- Incidence of Non-serious TEAEs by Maximum Relationship
- Incidence of TEAEs on or above Reporting Threshold of 5% (not for CSS)
- Incidence of Non-serious TEAEs on or above Reporting Threshold of 5% (not for CSS)

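### In the interim safety rules, the windows for counting adverse events and for time at risk do not match: 24 weeks is written as 160 days, and time is capped at day 112 for Initial Period discontinuers

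*SAP*

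**What the plan says.** **Combined Period, interim.** SAP 10.2 covers subjects who discontinue before Week 24 and whose safety follow-up visit falls beyond 24 weeks. For them the treatment-emergent period ends at 24 weeks, with the day count in brackets: "160 days) from the first study drug administration for the interim analysis". The matching time at risk for discontinuers in SAP 10.1.1 is a minimum of three terms, one of which is "168 days (equivalent to the intended 24-week treatment period".

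**Initial Period, interim.** For subjects who discontinue on or before the Week 16 visit, SAP 10.2 counts an AE that started "on or prior to the date of last administration of study medication + 70 days will be considered a TEAE for the analysis summaries". For the same subjects SAP 10.1.1 takes time at risk as the smallest of last dose + 70 days, "112 days (equivalent to intended 16-week Initial Period", and time to last clinical contact. Section 10.1 defines that contact as the latest of several dates, among them "last visit date including SFU visits".

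**The link.** SAP 10.2 takes its denominators from Section 10.1. The sentence beginning "The definitions for subject time at risk (in days) for the Initial Period" points there, and the next one makes those times the basis of the exposure-adjusted summaries. The exposure-adjusted incidence rate (EAIR) and event rate (EAER) are listed for the Initial Period and Combined Period AE tables.

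**Final analysis.** For Initial Period discontinuers SAP 10.1.2 uses the smaller of last dose + 70 days and time to last contact, with no 112-day term.

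**The concern.** An exposure-adjusted rate needs its events and its time taken from the same window. The interim rules break this in two places, in opposite directions. With a 160-day AE cut-off against a 168-day time cap, time is kept in which no event can count, so the rate is too low. With AEs counted to last dose + 70 days against a 112-day cap, events are kept that have no time behind them, so the rate is too high.

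The second mismatch also leaves the EAIR incompletely defined. SAP 10.2 sums each affected subject's time up to the first event. A first event after day 112 lies outside that subject's own time at risk, and the SAP does not say what to do with it.

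At stake are the interim exposure-adjusted AE rates. SAP 4.3 presents the interim as the full evaluation of the double-blind data, and discontinuers need not be spread evenly over the arms.

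**Working it through.** **Check of the plan's own conversions (weeks × 7).** SAP 10.1.1: 16 × 7 = 112, 8 × 7 = 56 and 24 × 7 = 168 all reproduce. SAP 10.2: 24 weeks written as 160 does not (160 / 7 = 22.86 weeks).

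**Combined Period.** Days are counted from first dose. If the number is taken literally, AE window end = min(last dose + 70, 160). Time at risk = min(last dose + 70, 168), with contact continuing that long.

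- Last dose Week 12 (day 84): 84 + 70 = 154 for both, gap 0.
- Last dose Week 14 (day 98): 98 + 70 = 168, so the AE window ends at 160 against 168 days of time, gap 8.
- Last dose Weeks 16 to 22: last dose + 70 exceeds 168, so again 160 against 168, gap 8.

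8 / 168 = 4.8% of such a subject's window. If the words govern, the limit is 168 and the gap is 0.

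**Initial Period.** SAP 10.1.1 fixes the last scheduled dose: "Week 14 is the intended last administration of study medication for this period". AE window end = last dose + 70. Interim time at risk = min(last dose + 70, 112), with contact continuing past day 112.

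| Last dose | AE window ends (day) | Interim time at risk (days) | Gap (days) | Gap / AE window |
|---|---|---|---|---|
| Week 6 (day 42) | 112 | 112 | 0 | 0% |
| Week 8 (day 56) | 126 | 112 | 14 | 11% |
| Week 10 (day 70) | 140 | 112 | 28 | 20% |
| Week 12 (day 84) | 154 | 112 | 42 | 27% |
| Week 14 (day 98) | 168 | 112 | 56 | 33% |

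Last doses before Week 6 also give no gap, because last dose + 70 is then below 112. Under the SAP 10.1.2 rule the gap is 0 in every row.

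These gaps are maxima. They shrink if contact ends before last dose + 70. SAP 4.3 also leaves out of the interim the data from a follow-up visit held after 24 weeks. The general interim cut-off in SAP 10.2, at the Week 24 visit, does not close the gap, since every window in the table ends by day 168.

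**Arm level (illustration only).** The documents give no dropout rate. Assume a share f of an arm discontinues with last dose at Week 14 and is followed to day 168, and everyone else contributes 112 days. Uncapped / capped denominator = [(1 − f) × 112 + f × 168] / 112 = 1 + f/2.

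- f = 2%: 1.01
- f = 10%: 1.05 (50 subjects: 5,880 / 5,600 days)
- f = 20%: 1.10

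For the same event count, the capped EAER would be 1% to 10% higher than the uncapped one. Last doses at Week 8 to 12 give less.

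**The case against.** **The 160 is a visible slip.** The same sentence states the limit in words as 24 weeks, SAP 4.3 gives the same limit with no day count, and every other conversion is right. A reader might infer that AEs on days 161 to 168 were in fact dropped and that Combined Period rates are understated. The documents do not show that; it follows only if the number was programmed. What stands is that an operative cut-off carries two values and only one agrees with the denominator.

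**The interim has been run and the final rule is already right.** SAP 9.3 to 9.5 cite interim results. SAP 12.2 says that Amendment 2 leaves the interim analyses alone, that Section 10.1 was updated to remove inconsistencies, and that 10.1.1 keeps the interim rules while 10.1.2 holds the new ones for the final analysis. This is correct, and it confines the point to the interim rates. It does not make those rates internally consistent.

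**Cutting AEs at day 112 would reconcile the windows equally well,** since SAP Table 3-1 ends the Initial Period at Week 16. That is true arithmetically, but the interim would then differ from the final rule.

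**SAP 4.3 says the Initial Period analyses are the same as for the final CSR.** A reader might call the 112-day cap a flat contradiction of this. In context, between sentences on the escape arm and on the Blinded Maintenance Set, the statement may only describe scope, so little weight is put on it here.

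**Conclusion.** The point holds for the interim safety rules as written. The 160 should be 168; its effect is 8 days per affected subject if the number was programmed and nil if the words were. It concerns discontinuers with last dose at about Week 14 to 22 and follow-up past Week 24. The 112-day cap leaves up to 14 to 56 days per subject with events but no time, for last doses at Week 8 to 14 with contact past day 112. Interim Initial Period EAIR and EAER can therefore be biased upward and can differ from the final rates for the same subjects. By how much depends on the unstated number of such discontinuers and on whether any AEs start after day 112.

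Three stronger readings are not supported:

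- Rates are not simply inflated in the arm with more early discontinuations, because the earliest discontinuers (last dose Week 6 or before) have no gap.
- The 11% to 33% figures are shares of one subject's AE window, not the bias in an arm's rate.
- Neither the primary efficacy analysis nor the final Initial Period rates are touched.

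This is a minor, cheap correction to descriptive tables.

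**What to change.** 1. In SAP 10.2, Combined Initial and Maintenance Period, change 160 to 168 days, and confirm from the interim programs which cut-off was used.
2. For interim Initial Period discontinuers, use the SAP 10.1.2 denominator: the smaller of last dose + 70 days and time to last contact, with AEs and time both cut at day 168.
3. Because the interim has been run, choose one of two routes. Either rerun the affected exposure-adjusted tables under that rule and document it as a correction, or leave 10.1.1 as the record of what was done and state in the final CSR that the interim rates used the 112-day cap and are superseded by the final Initial Period rates. If the program check shows 160 was used, say so in the same place.

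The cost is one number, one denominator rule already written elsewhere in the SAP, and either a rerun of a few descriptive tables or a short note in the CSR.

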10.3 Clinical laboratory evaluations

Definitions and Data Handling Conventions

The following table indicates the laboratory data that will be collected. Note that hematology and chemistry data will be summarized in tables. Urinalysis data will be listed only.

Table 10–1: Laboratory parameters to be collected

Hematology	Chemistry	Urinalysis
Basophils	Calcium	Albumin
Eosinophils	Chloride	Bacteria
Lymphocytes	C-reactive protein	Crystals
Atypical lymphocytes	Magnesium	Glucose
Monocytes	Potassium	pH
Neutrophils	Sodium	Red blood cells (RBC)
Hematocrit	Glucose	White blood cells (WBC)
Hemoglobin	Urea nitrogen	Urine dipstick for pregnancy testing ^a
Mean corpuscular hemoglobin (MCH)	Creatinine	
Mean corpuscular hemoglobin concentration (MCHC)	Alkaline phosphatase (ALP)	
Mean corpuscular volume (MCV)	Aspartate aminotransferase (AST)	
Platelet count	Alanine aminotransferase (ALT)	
RBC count	Gamma glutamyl transferase (GGT)	
WBC count	Bilirubin	
	Lactate dehydrogenase (LDH)	
	Cholesterol	
	Albumin	
	1,3 Beta-D-glucan	
	KL-6	
	Hepatitis B surface antigen ^b	
	Hepatitis B core antibody ^{b,c}	
	Hepatitis B surface antibody ^{b,c}	

Table 10–1: Laboratory parameters to be collected

Hematology	Chemistry	Urinalysis
	Hepatitis type B virus DNA ^c	
	Hepatitis type C virus antibody ^b	
	Human immunodeficiency virus antigen ^b	
	Human immunodeficiency virus antibody ^b	
	T-cell lymphotropic virus type-1 antibody ^b	
	Serum pregnancy testing ^a	

^a Pregnancy testing will consist of serum testing at Screening. The pregnancy test will be urine at all other visits.

^b Performed at Screening only

^c If the subject is either HBs antibody-positive or HBc antibody-positive at Screening, quantitative measurement of HBV-DNA should be performed every 4 weeks from Baseline to Week 52 and at SFU.

The following parameters will not be included in the chemistry tables:

- Hepatitis B surface antigen
- Hepatitis B core antibody
- Hepatitis B surface antibody
- Hepatitis B virus DNA
- Hepatitis C virus antibody
- Human immunodeficiency virus antigen
- Human immunodeficiency virus antibody
- T-cell lymphotropic virus type-1 antibody
- Serum pregnancy testing

Values by visit will only be listed.

Markedly abnormal laboratory values will be defined as those categorized as Grade 3 or higher based on the Rheumatology Common Toxicity Criteria (RCTC) v2.0 (Woodworth et al, 2007). Definitions of markedly abnormal values for hematology and chemistry using the Grade 3 cut points are provided below

Table 10–2: Definitions of markedly abnormal hematology values

Parameter (SI units)	Markedly abnormal low	Markedly abnormal high
Hemoglobin (g/L)	< Lower Limit of Normal (LLN) AND decrease from Baseline >20	Not applicable
Hemoglobin (g/L)	<80	Not applicable
Leukocytes (total x 1000)	<2.0	Not applicable
Lymphocytes (x 1000) ^a	<0.5	Not applicable

Table 10–2: Definitions of markedly abnormal hematology values

Parameter (SI units)	Markedly abnormal low	Markedly abnormal high
Neutrophils (x 1000)	<1.0	Not applicable
Platelets (x 1000)	<50	Not applicable

^a For lymphocytes, the Grade 3 CTCAE cut point is used as the RCTC Grade 3 cut point (<1.0) is higher than the lower limit of normal (0.8) specified by the lab.

Table 10–3: Definitions of markedly abnormal chemistry values

Parameter (SI units)	Markedly abnormal low	Markedly abnormal high
ALT (U/L)	Not applicable	>3x ULN
AST (U/L)	Not applicable	>3x ULN
Calcium (mmol/L)	<1.75	>3.125
CPK (U/L)	Not applicable	>4x ULN
Glucose (mmol/L)	<2.22	>13.89
Potassium (mmol/L)	<3.0	>6.4
Sodium (mmol/L)	<125	Not applicable
Total bilirubin (µmol/L)	Not applicable	≥2x ULN

For tables where data are summarized by visit, unscheduled and repeat visits will not be summarized, but these data will be included in listings. For tables where multiple measurements over a period of time are considered (as in shift tables), unscheduled and repeat visits will be considered as long as they were collected in the period being summarized. All laboratory summaries will be presented in SI units and will be based on observed case values. In the case where laboratory values are below the lower limit of quantification, then these will be set to the lower limit of quantification divided by 2 for the purpose of summarizing the data.

The criteria for meeting Hy’s Law are defined as follows:

- ≥3xULN ALT or AST with coexisting ≥2xULN total bilirubin in the absence of ≥2xULN ALP.

In order to meet the above criteria, a subject must experience the elevation in bilirubin and ALT or AST at the same visit. For example, a subject who experiences a ≥2 x ULN elevation of bilirubin at one visit and a 3 x ULN elevation in ALT (or AST) at a subsequent visit has not fulfilled the Hy’s law criteria.

Other liver function test elevations that are of interest for summary purposes are:

- 3x, 5x, 8x ULN elevations of AST,
- 3x, 5x, 8x ULN elevations of ALT,
- 3x, 5x, 8x ULN elevations of either AST or ALT,
- 1x, 1.5x ULN elevations of Bilirubin
- 3x ALP

For determining cases of Hy's Law and other liver function test elevations, only post-Baseline assessments are considered. Pre-treatment and Safety Follow-up assessments are excluded. Additionally, assessments collected more than 70 days after the last dose of study treatment are excluded.

Lab Data Summary by Period

Initial Period

All summaries for the Initial Period will be presented by treatment group for the SS and the CSS.

Hematology and chemistry absolute and change from Baseline values will be summarized by visit using descriptive statistics for continuous data. In addition, the summaries will include descriptive statistics within the Initial Period for the end of treatment, minimum post-Baseline, and maximum post-Baseline values.

Shift from Baseline tables for lab values based on the normal range will be presented within the Initial Period for the end of treatment, minimum post-Baseline and maximum post-Baseline values. The shift categories will be low, normal, high, and missing.

The number and percent of subjects with markedly abnormal (\geq grade 3 by CTCAE) hematology or chemistry values will be summarized by visit and for any visit during the Initial Period. For the "any visit" summary, only values while on study treatment will be considered, meaning that the Baseline measurement will not be considered.

Shift from Baseline tables for lab values based on the markedly abnormal lab values will be presented within the Initial Period for the end of treatment, minimum post-Baseline, and maximum post-Baseline. The shift categories will be markedly abnormal, not markedly abnormal, and missing.

The number and percent of subjects meeting Hy's law criteria and other liver function test elevations specified above at any visit while on study treatment (i.e., Baseline excluded) during the Initial Period will be summarized.

Combined Initial and Maintenance Period

The summaries described above for the Initial Period will be repeated for the Combined Initial and Maintenance Period and will be presented based on the SS and CSS. For the summaries based on the SS, the tables that are produced will include data while on either blinded or open-label treatment.

For the markedly abnormal values summary by visit, the percentage will be based on the number of subjects with observed values at the given visit. Therefore, the denominator will vary based on the visit. For the "any visit" summary, this will be based on all observed values.

Shift from Baseline tables for markedly abnormal lab values will be presented for the Combined Initial and Maintenance Period relative to the end of treatment, minimum post-Baseline, and maximum post-Baseline values. The shift categories will be markedly abnormal, not markedly abnormal, and missing.

If a subject switches blinded CZP dose from Initial to Maintenance Period, the minimum post-baseline value, the maximum post-baseline value and the end of treatment value will be determined for each respective dose received. For the summarization of "All CZP", the minimum and maximum post-baseline value will be determined considering values reported

while on either CZP dose; the end of treatment value will reflect the values reported while on the last CZP dose received during the study.

The shift table will present shifts by treatment group from Baseline (last observation before Week 0; regardless of which study treatment was administered at Week 0) to post-Baseline minimum, maximum and end of treatment while on treatment summarized. Values observed during blinded and open-label are included.

The number and percent of subjects meeting Hy's law criteria and other liver function test elevations specified above at any visit while on blinded or open-label study treatment (ie, Baseline excluded) during the Combined Initial and Maintenance Period will be summarized.

